• The IRB will not accept grant applications and/or sponsor's protocols in lieu of the items as outlined below.

- Do not separate responses from items. Instead, insert your response to each item below the item, keeping the information in the order of this form.

14. Purpose - in nontechnical, lay language

- Summarize the purpose and objectives of this protocol in one short paragraph. The purpose of this study is to determine if Intranasal Ketamine (INK) is efficacious for Procedural Sedation and Analgesia (PSA) when compared to Intravenous Ketamine (IVK) in children with non-operative fractures. The primary aim is to determine if INK provides non-inferior sedation to IVK as defined by a Modified Ramsay Sedation score of ≥ 4 and also to compare the proportion of successful procedure between two treatment groups. The secondary aim is to compare proportion of adverse events and compare duration of sedation and length of ED stay between treatment groups.
- Describe how outcomes will be measured for this protocol. The outcome measured in this study will be successful sedation as defined by Modified Ramsay Sedation score of ≥ 4 . Successful competition of procedure will be defined as completing the procedure with the induction dose and without requiring rescue medication. Any adverse events related to sedation will be documented. Duration of sedation will be the time from administration of induction (first dose) Ketamine to Aldrete score reaching baseline or pre-sedation. ED length of stay will be defined as time to arrival to ED to time of discharge order from ED physician.

15. Background - in nontechnical, lay language

- Summarize in 2-3 paragraphs past experimental and/or clinical findings leading to the design of this protocol. Include any relevant past or current research by the PI. For drug and device studies, summarize the previous results (i.e., Phase I/II or III studies).

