dedicated automated medication dispensing system in the ED. These syringes will be pre-labelled by a color code without identifying the drug inside. Color code indicates the route of administration (Intranasal or Intravenous). Treatment allocated to the patient will only be known to the research pharmacist. Research pharmacist will maintain a log of randomization ID and patient identifier. Study drugs will be discarded at the conclusion of the sedation per our ED protocol. Sedating physician will document randomization ID in their sedation record. Study pharmacist will use pyxis data entry and documentation to verify drug administration and drug dosage.

Breaking the blinded code:

We do not anticipate any serious adverse events and need for premature code breaking. After all patients are enrolled and data entry is complete, we will break the blinded code just before data analysis.

Sedation induction and monitoring:

Subject randomized to the IN ketamine will receive IN Ketamine. After 8 minutes, IV Normal Saline (NS) will be given over 30 seconds. Subjects randomized to IV Ketamine will first receive IN hypertonic (3%) saline. After 8 minutes, IV Ketamine will be given over 20-30 seconds.

The study personnel will assess the level of sedation at 5-minute intervals, per our ED protocol, after IN medication administration (induction dose) using the modified Ramsay sedation scale until a score of ≥ 4 is achieved, which will serve as our definition of adequate sedation. Modified Ramsay Sedation scale scores range from 1-8 based on wakefulness of the patient. Score of 1 indicates fully awake and alert whereas score of 8 indicates unresponsive to external stimuli including pain. This scoring will be done by trained study personnel. Sedation scoring will be continued at 5-minute intervals until the reduction is completed. Failure of sedation will be defined as not achieving adequate sedation by Ramsay score of < 4 within 10 minutes of IN administration.

Patients who fail sedation at 10 minutes will receive 0.5 mg/kg IV ketamine or more, with additional IV doses as deemed necessary by treating physician. No subsequent IN medications will be given after the induction dose. Duration of successful sedation will be defined as induction dose time to when the patient is appropriate for discharge from sedation as noted by sedating ED physician. Discharge criteria includes patient said to have reached baseline/pre-sedation modified Aldrete Score.

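### Sedation success has two conflicting rules on rescue, and duration of sedation has two start times that differ by 8 minutes in the IV arm only

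*Combined protocol and SAP*

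**What the plan says.** **Section 14 (Purpose).** The primary aim is non-inferior sedation: "The outcome measured in this study will be successful sedation as defined by Modified Ramsay Sedation score of" 4 or more. There is no time limit. Rescue appears only in a second outcome, successful completion of the procedure, which the same paragraph also places in the primary aim. Duration runs from the first ketamine dose until the Aldrete score is back to baseline.

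**Section 17.a, Sedation induction and monitoring.** Scores are timed from the intranasal syringe, which the text labels the induction dose: "The study personnel will assess the level of sedation at 5-minute intervals, per our ED protocol, after IN medication administration (induction dose". It uses the term the same way again: "No subsequent IN medications will be given after the induction dose". In the IV arm the first syringe contains no ketamine: "Subjects randomized to IV Ketamine will first receive IN hypertonic (3%) saline. After 8 minutes, IV Ketamine will be given over 20-30 seconds". The failure rule is "Failure of sedation will be defined as not achieving adequate sedation by Ramsay score of < 4 within 10 minutes of IN administration", and rescue is not part of it. Duration has a different start here: "Duration of successful sedation will be defined as induction dose time to when the patient is appropriate for discharge from sedation".

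**Section 17.a, Procedure.** A failed sedation is a score below 4 by 10 minutes from the induction dose, or any rescue dose of IV ketamine during the procedure. The text says rescue is often required and would not ordinarily be called a failure, but is counted here because the two induction doses are being compared.

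**The concern.** The same child can be a success or a failure on the primary sedation outcome, depending on which section the analyst follows. By the protocol's own account rescue is frequent, so this is not a rare case. Under the Procedure rule, sedation success also becomes nearly the same thing as procedure success, although section 14 lists them as two parts of the primary aim.

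The code is to be broken just before analysis. A definition still open at that point could be settled with the results in view. The duration comparison has a related defect: one of its two clocks includes 8 minutes in which the IV arm has had no ketamine.

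**Working it through.** **No figure to reproduce.** The plan gives 70 children, 35 per arm, without a margin, alpha, power or expected rates. The first three steps below use the documents only. Step 4 and the test percentages in step 3 rest on stated assumptions.

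**1. Classification of the same child under each passage**

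| Child | Section 14 | 17.a Sedation induction | 17.a Procedure |
|---|---|---|---|
| Reaches 4 by minute 10, never rescued | success | success | success |
| Reaches 4 by minute 10, rescued later | success | success | **failure** |
| Below 4 to minute 10, rescued, then reaches 4 | success as worded (no window) | failure | failure |

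The second row is the main contradiction. It does not depend on how the clock is read. Under the third column, a sedation success is a child who reaches 4 in time and needs no rescue. Procedure success is completion without rescue. The two therefore largely coincide.

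**2. Scores under ketamine inside the window.** Scores fall at minutes 5, 10, 15 and so on after the intranasal syringe. Ketamine starts at minute 0 in the IN arm and minute 8 in the IV arm. Within 10 minutes of intranasal administration:

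- IN arm: minutes 5 and 10, two scores.
- IV arm: minute 10 only, which is 10 − 8 = 2 minutes after the push starts.

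The extra IN score changes a result only for a child at 4 or more at minute 5 and below 4 at minute 10. The documents give no basis for that share, and it may be near zero.

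**3. Duration.** Let T be the minutes from the intranasal syringe to sedation discharge.

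- Section 17.a clock: T in both arms.
- Section 14 clock: T in the IN arm, T − 8 in the IV arm.
- Difference between clocks: 0 minutes (IN), 8 minutes (IV).

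The effect on a test depends on the SD, which is not given. Assume SDs of 15, 20 or 30 minutes, no true difference, 35 per arm and a two-sided 5% t-test. The standardised shift is 8/SD = 0.53, 0.40 or 0.27, and it alone gives p < 0.05 in 59.5%, 37.8% or 19.6% of trials. If only successful sedations are analysed, as the 17.a wording suggests, the figures fall; with 22 and 28 children, for example, they are 45%, 28% and 15%.

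**4. Rescue rule and the primary test (all rates assumed).** A proportion r = 0.90 or 0.95 reaches 4 in each arm. Of these, 10% in each arm are later rescued. The test is Farrington-Manning at one-sided 2.5%, by exact binomial enumeration with n = 35 per arm.

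- Success on Ramsay alone: r = 0.90 or 0.95.
- Success on Ramsay plus no rescue: r × 0.90 = 0.81 or 0.855.
- Children who change class, per arm: 35 × r × 0.10 = 3.2 to 3.3.

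| Margin (assumed) | r | Ramsay alone | Ramsay plus no rescue |
|---|---|---|---|
| 15 points | 0.90 | 45.2% | 34.0% |
| 15 points | 0.95 | 63.4% | 37.9% |
| 20 points | 0.90 | 74.1% | 56.8% |
| 20 points | 0.95 | 89.7% | 63.9% |

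The arms are truly equal in every row. The fall in power comes only from the lower success rate and its larger variance.

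**The case against.** The strongest reply is that the Procedure paragraph is deliberate: it announces a definition for the study's own purposes and gives a reason. Section 14 is a short summary, and it already brings rescue into the primary aim through procedure success. That lessens the consequence, because rescue enters one primary comparison either way. It does not remove the contradiction. Nothing says that the Procedure rule replaces the section 14 definition, and the other part of 17.a sides with section 14.

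Four stronger readings are tempting, and the documents do not support them.

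- **That the choice of rule decides the trial.** A large swing appears only if IN children are assumed to be rescued much more often than IV children. That builds in a true IN deficit, and a failed non-inferiority test is then largely the test doing its job. No rescue rate by arm is given.
- **That the 2 v 1 scores bias the trial toward IN.** The direction is right for a Ramsay-only outcome, but the size cannot be derived.
- **That the window has three rival definitions.** "Patients who fail sedation at 10 minutes" most naturally says when the consequence of failure applies. A window running from IV ketamine in the IV arm has one sentence in its favour, where the Procedure paragraph speaks of an IV induction dose. Shortly before, that paragraph attaches the word induction to the intranasal drug. Blinded staff also could not run an arm-specific clock.
- **That an early score of 4 or more unmasks the arm.** Prior pain medication could produce such a score in the IV arm, and the direction of any resulting bias is undetermined.

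The attached data collection sheet is not available here and may settle some time stamps.

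**Conclusion.** The point holds as two contradictions and one lesser ambiguity. The rescue conflict changes the class of every child who reaches 4 in time and is rescued later. The duration conflict is 8 minutes, in the IV arm only. Both follow from the text without any assumption, and nothing in the documents resolves either. The uneven number of scores in the 10-minute window is real on the plainest reading, but its effect is unknown and may be negligible.

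The range of 45-90% against 34-64% for claiming non-inferiority shows that the definition can matter even when the arms are equal. It depends on the assumed margin, response rates and 10% rescue rate, and is not an estimate for this trial. The wording should be corrected before analysis; the finding does not show that the design is invalid.

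**What to change.** Before the code is broken, and without altering any dosing or rescue rule:

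1. Reconcile section 14 and both parts of section 17.a to one analysis definition of sedation success, named as primary: either Ramsay alone, or Ramsay plus no rescue. State one time origin for the 10-minute window. Report the other definition as a sensitivity analysis.
2. Start duration at the first ketamine dose in both arms, as section 14 has it, and make section 17.a agree.
3. Report the Ramsay and rescue components separately by arm.

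The cost is wording and one extra table. Interval scores, time to sedation, rescue use and duration are already on the section 17.a data collection list. The drawback is that the two definitions may disagree; naming the primary in advance settles which one carries the conclusion.

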Procedure: Once sedation is achieved, orthopedic surgeon will start the fracture reduction. Depending on the type of fracture, length of reduction varies from 5-60 minutes. This includes cast placement and molding which can be painful and is to be included as part of the procedure. Successful completion of procedure will be defined as completed reduction and casting as deemed necessary by orthopedist using only the first 2 drug doses that include the induction intranasal drug and IV drug given at the 8-minute mark. For our purposes, a failed sedation will be described as modified Ramsay sedation score of < 4 by 10 minutes from induction dose or where the patient requires a rescue dose of IV Ketamine at any time throughout the procedure as deemed necessary by sedating physician. Rescue doses are often needed and are not generally documented or referred as "failed" sedation. However, we are directly comparing the induction dose of IN Ketamine to induction dose of IV ketamine. The treating ED physician will assess the outcome and either conclude the sedation as failed or successful. After the procedure is completed, the ED physician will assess and deem the patient appropriate for discharge once the patient has been said to have reached baseline/pre-sedation modified Aldrete Score.

Data collection:

We will collect clinical and demographic variables (Attached Data collection sheet).

Clinical variables collected will include patient age, patient weight, imaging obtained, the type of fracture, mechanism of fracture, location of fracture, time of injury, NPO status, prior pain medication administration and time, other associated presenting symptoms, medical history, surgical history, allergies, time to sedation, sedation scores and vital signs at each interval set by ED protocol, whether rescue medication was needed, type of casting placed, adverse events, non-sedation-related delays (c-arm/radiology, casting supplies, nursing, ortho, etc), reduction failure not related to a sedation complication, duration of sedation, sedation discharge score, ED length of stay. Demographic information such as age, gender, race/ethnicity, ED arrival date/time.

Duration of study:

The total duration of the study will be 2 years including enrollment, data collection, and data analysis and writing report.

- b.** What is the probable length of time required for the entire protocol (i.e., recruitment through data analysis to study closure)? 24 months

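### Sedation duration, a secondary outcome, has an ambiguous start point; one of its two readings adds about 8 minutes to the IV ketamine arm only

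*Combined protocol and SAP*

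**What the plan says.** Section 14 gives the secondary aim, in part, as to "compare duration of sedation and length of ED stay between treatment groups". Its answer on how outcomes are measured reads "Duration of sedation will be the time from administration of induction (first dose) Ketamine to Aldrete score reaching baseline or pre-sedation".

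Section 17.a, under Sedation induction and monitoring, defines the outcome again: "Duration of successful sedation will be defined as induction dose time to when the patient is appropriate for discharge from sedation". The end points agree in substance, because the discharge criteria there include return to the pre-sedation modified Aldrete score. The start points are worded differently.

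The same subsection says sedation is scored "after IN medication administration (induction dose) using the modified Ramsay sedation scale". It sets the IVK sequence as "Subjects randomized to IV Ketamine will first receive IN hypertonic (3%) saline. After 8 minutes, IV Ketamine will be given over 20-30 seconds". In INK the intranasal dose is ketamine and the IV dose at 8 minutes is normal saline.

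The Data collection paragraph of 17.a lists "duration of sedation, sedation discharge score, ED length of stay" among the variables to be collected. On unblinding, the plan says "After all patients are enrolled and data entry is complete, we will break the blinded code just before data analysis".

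**The concern.** The two definitions give the same duration in INK. They can differ in IVK, where the first dose in the sequence contains no ketamine. If the clock starts at the intranasal dose, each IVK duration carries a lead-in of about 8 minutes that belongs to the blinding schedule and not to the drug. The lead-in always acts in the same direction, so it could be reported as shorter sedation with INK even if recovery from the active drug were identical.

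Blinding makes this a practical matter. Bedside and study staff do not know which dose was ketamine, and data entry closes before the code is broken. A single duration entered at the bedside therefore cannot be timed from the first ketamine dose as such. The start has to be assigned later, from recorded dose times.

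**Working it through.** The plan states no figure for this outcome (no SD, test, alpha or target difference), so there is none to reproduce. The check has three steps.

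**1. What the induction dose means in the plan**

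Uses that point to the intranasal dose in both arms:
- Section 17.a, Sedation induction and monitoring, puts the term in brackets directly after the intranasal administration.
- The sentence before the duration definition says no further intranasal drug follows the induction dose.
- Failure is a Ramsay score below 4 within 10 minutes of the intranasal administration in one paragraph, and by 10 minutes from the induction dose in the Procedure paragraph. These agree in both arms only if the two events are the same.
- The Procedure paragraph defines success as completion "using only the first 2 drug doses that include the induction intranasal drug and IV drug given at the 8-minute mark".

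Uses that cover IV ketamine:
- Section 14 defines a successful procedure as one completed with the induction dose and no rescue. In IVK that must include the IV ketamine.
- Section 17.a, Recruitment and Enrollment, calls 1.5 mg/kg IV an induction dose.
- The Procedure paragraph compares the induction doses of IN and IV ketamine.
- The table in Section 17.e labels sedation induction as IV or IN ketamine.

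**2. Timeline (minutes from the intranasal dose; R = time of return to baseline)**

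| | INK | IVK |
|---|---|---|
| First ketamine | 0 | 8 |
| Duration from first ketamine (Section 14) | R | R − 8 |
| Duration from intranasal dose (Section 17.a usage) | R | R |
| Difference between clocks | 0 | 8 |

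Changing the clock moves the IVK minus INK contrast by 8 − 0 = 8 minutes.

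**3. How often 8 minutes alone would reach p<0.05**

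From the plan: 8 minutes (Section 17.a) and 35 per arm (Section 16.e). Assumed: the SD, a two-sided t-test at 0.05, and equal durations from active drug.

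Standard error = SD × √(1/n₁ + 1/n₂). Noncentrality = 8 / standard error. Degrees of freedom = n₁ + n₂ − 2. The rejection rate comes from the noncentral t distribution. Example at SD 15 with 35 per arm: 15 × √(2/35) = 3.59; 8 / 3.59 = 2.23; df 68; rate 0.595.

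| Assumed SD | SE, 35/35 | Noncentrality | Rate, 35/35 | Rate, 20 INK / 30 IVK |
|---|---|---|---|---|
| 15 | 3.59 | 2.231 | 0.595 | 0.44 |
| 20 | 4.78 | 1.673 | 0.378 | 0.27 |
| 30 | 7.17 | 1.116 | 0.196 | 0.15 |
| 40 | 9.56 | 0.837 | 0.131 | 0.10 |

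Almost all of these rejections show INK as shorter (0.128 of the 0.131 at SD 40). Simulation with normal and gamma-distributed durations agreed to within 0.01 for 35 per arm.

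The last column applies if only successful sedations are compared, as the wording of Section 17.a suggests. The counts of 20 and 30 are assumed for illustration.

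The SD 15 row is best taken as an upper case. The plan puts the reduction at 5 to 60 minutes. If that were uniform (assumed), its SD alone would be 55/√12 = 15.9 minutes, before variation in recovery is added.

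The null can also be turned round. If total time from the intranasal dose were equal in the two arms, a clock started at ketamine would show IVK shorter by 8 minutes, with the same rejection rates by symmetry.

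**The case against.** The strongest reply is that nothing is wrong once Section 17.a is read in the light of Section 14. Section 14 answers the form's question on outcome measurement and names ketamine as the start. Several other places treat IV ketamine as an induction dose. On that reading Section 17.a is shorthand and the offset is zero. This stands to the extent that the plan does not plainly contradict itself: a reader might infer that IVK durations will certainly be 8 minutes too long, and the mixed usage does not support that. It does not remove the problem, because two careful analysts could follow the plan and obtain different IVK durations.

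A second reply is that the rejection rates rest on assumptions. That is right. Only the 8 minutes comes from the plan. The SDs are assumed, equal duration from active drug is assumed although dose and route differ, and 35 per arm is too many if only successful sedations count.

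A third reply is that the scheduled 8 minutes could be subtracted in IVK after unblinding. That works if every entry was timed from the intranasal dose and the schedule was kept; recorded times need neither condition. A reader might also infer that the IV dose times will be lost. The documents cannot show this, because the data collection sheet is an attachment that is not among them.

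Finally, a common clock from the intranasal dose is defensible, since sedation scoring and the 10-minute failure rule already use it in both arms. But the plan does not argue for it as the duration clock, and Section 14 names a different start.

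**Conclusion.** The point holds as an ambiguity in a secondary outcome. Section 14 starts the clock at the first ketamine dose. Section 17.a starts it at an induction dose that the subsection mostly identifies with the intranasal administration, while other parts of the plan extend the term to IV ketamine. The size is about 8 minutes in IVK only on the Section 17.a usage, and zero if that section is read to match Section 14.

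The chance that the offset alone gives p<0.05 is about 13% to 59% for assumed SDs of 40 down to 15 minutes with 35 per arm, and about 10% to 44% with an assumed 20 INK and 30 IVK successes. These figures illustrate the stakes and do not predict the result.

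A reader might carry the concern over to the primary outcome. The duration clock does not enter it: the primary aim concerns the Ramsay score and successful procedures. The correction is worth making because it is specific, inexpensive and removes a one-sided offset from a stated comparison.

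**What to change.** Use the Section 14 definition in both sections, worded for example as: time from the active ketamine dose (the intranasal time in INK, the start of the IV push in IVK, assigned after the code is broken) to return to the baseline modified Aldrete score.

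Record the actual intranasal and IV dose times for every child, if the data sheet does not already do so. Report time from the intranasal dose as a sensitivity analysis, so that the reader can see both clocks. State also whether duration is compared in all randomised children or only in successful sedations, since Section 17.a limits it to the latter and Section 14 does not.

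The cost is a wording change, one derivation after unblinding and, at most, two extra times on the data sheet. Sample size and blinding stay as they are. The small downside is that the contrast will look less favourable to INK than under the Section 17.a usage.

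### Duration of sedation has two unreconciled ends, Aldrete return to baseline and a discharge note made after casting, so a child who recovers mid-procedure can be recorded with the time to the procedure's end.

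*Combined protocol and SAP*

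**What the plan says.** Section 14 lists, among the secondary aims, to "compare duration of sedation and length of ED stay between treatment groups". Its outcome paragraph then gives a definition: "Duration of sedation will be the time from administration of induction (first dose) Ketamine to Aldrete score reaching baseline or pre-sedation".

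Section 17.a (Sedation induction and monitoring) gives another. There the duration of successful sedation runs from "induction dose time to when the patient is appropriate for discharge from sedation as noted by sedating ED physician". The next sentence links this to the score without making the score the event: "Discharge criteria includes patient said to have reached baseline/pre-sedation modified Aldrete Score".

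Section 17.a (Procedure) says when the assessment takes place: "After the procedure is completed, the ED physician will assess and deem the patient appropriate for discharge once the patient has been said to have" returned to the pre-sedation score. The same paragraph counts cast placement and molding as part of the procedure and states: "Depending on the type of fracture, length of reduction varies from 5-60 minutes".

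On data, section 17.a schedules modified Ramsay scoring every 5 minutes until the reduction is complete. The Data collection paragraph lists sedation scores and vital signs at each interval set by the ED protocol, non-sedation delays such as C-arm and casting supplies, and then "duration of sedation, sedation discharge score, ED length of stay". It names no separate time of Aldrete return. It refers to an attached data collection sheet that is not in the text available.

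**The concern.** Aldrete return describes how long the drug acts. A discharge note that is made only once the cast is on depends on the drug and on the procedure, whichever takes longer. The procedure's length reflects the fracture, the orthopaedic work and waits for equipment, none of which is an effect of the route of ketamine.

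If the note supplies the end time, the recorded duration has a floor at the end of the procedure. On a common clock, a floor that is similar in both arms pulls the arm means together, so two routes with different recovery times can look alike. If the end is left open, someone must also choose between the two definitions at analysis. If the time of Aldrete return was not written down at the bedside, that choice is no longer available.

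**Working it through.** The plan gives no figure for this outcome to reproduce: no expected duration, SD, power or significance level. The check therefore has three steps.

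**1. The two definitions side by side.** Let R be the time from induction to Aldrete return, t0 the start of the procedure and P its length.
- Section 14: duration = R.
- Section 17.a, with the assessment after the procedure: duration is at least max(R, t0 + P).

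They agree when R ≥ t0 + P and the note is prompt. They differ when R < t0 + P.

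**2. Single records.** P comes from the stated 5 to 60 minutes; t0 = 10 minutes is an assumption.

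| R | P | Section 14 | Section 17.a, at least | Excess |
|---|---|---|---|---|
| 30 | 15 | 30 | max(30, 25) = 30 | 0 |
| 60 | 40 | 60 | max(60, 50) = 60 | 0 |
| 30 | 40 | 30 | max(30, 50) = 50 | 20 |
| 30 | 60 | 30 | max(30, 70) = 70 | 40 |

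A delay during the procedure adds directly. With R = 30, a 50-minute procedure gives 60, and a further 20-minute C-arm or casting delay gives 80.

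**3. Effect on the comparison of arms.**
- From the documents: 35 per arm (section 16.e); P between 5 and 60 minutes (section 17.a).
- Assumed: P uniform over that range, t0 = 10 minutes in both arms, R lognormal with SD 15 minutes, a true difference of 10 minutes, both clocks started at the intranasal syringe, no rescue.
- Recorded value: D = max(R, 10 + P).
- Power: Φ(difference / √((s1² + s2²)/35) − 1.96), where s1 and s2 are the arm SDs.

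Without a floor: √((225 + 225)/35) = 3.59; 10/3.59 − 1.96 = 0.83; power about 80%. With the floor, by simulation:

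| Mean R, two arms (min) | Share set by the procedure | Recorded difference (min) | Power |
|---|---|---|---|
| 30 v 40 | 73% and 55% | 3.6 | 18% |
| 40 v 50 | 56% and 38% | 5.3 | 36% |
| 50 v 60 | 38% and 23% | 7.0 | 58% |
| 60 v 70 | – | 8.4 | 71% |
| 80 v 90 | 4% and 1% | 9.8 | 79% |

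At 90 v 100 the recorded difference is 10.0. A different assumed shape gives the same picture: with normal recovery times, SD 10 to 15 and a 15-minute difference, the recorded difference is 6.2 minutes at 30 v 45 and 14.9 to 15.0 at 90 v 105.

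If half of the children who recover early are rescued and left out, the recorded differences for the first three rows become 3.7, 5.9 and 7.5 minutes.

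**The case against.** The strongest reply is that the definitions share their main ingredient. Section 17.a makes baseline Aldrete a discharge criterion, so they part only for a child who is back at baseline before the cast is finished. The protocol itself suggests that this group may be small: casting can be painful, rescue doses are described as often needed, any rescue counts as failed sedation, and the section 17.a definition is worded for successful sedation. This stands as a limit on how many children are affected. It does not remove the conflict, because rescue is left to the sedating physician's judgement and the protocol does not say how rescued children enter the duration analysis.

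Rescue also changes the benchmark. If 90% of early recoverers are left out (40 v 50 minutes), the recorded difference is 6.9 minutes, but even a perfect Aldrete clock would give only 8.1. The floor then costs 8.1 − 6.9 = 1.2 minutes; the rest is selection.

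A reader might infer that the time of Aldrete return is never recorded. The documents do not establish that. The interval sedation scores follow an ED protocol that is not shown, the data sheet is not shown, and section 17.e lists sedation monitoring from induction to ED discharge, as both research and routine care. Even if the times exist, the two definitions still disagree on which one to use.

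A reader might also infer that intranasal ketamine will falsely appear longer-acting. That needs a different conflict, over the start of the clock: section 14 starts at the first ketamine, which the intravenous arm receives 8 minutes after the intranasal syringe. With equal recovery (40 v 40 minutes) and that start, an excess of 3.5 to 3.9 minutes appears, but only if intranasal procedures begin at minute 10; it falls to 1.2 to 1.4 if they begin at minute 5. It is not a consequence of the two ends.

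**Conclusion.** The conflict is real and does not depend on the simulation: a secondary outcome has two stated ends, and one of them cannot come before the procedure is over. Neither can be called the intended one and the other a slip, since the protocol states both.

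The size is unknown. Under the stated assumptions a true 10-minute difference is recorded as anything from 3.6 minutes (mean recovery 30 v 40) to 9.8 (80 v 90), depending on how recovery compares with procedure length, and rescue of early wakers lowers the number affected. The fall in power from 80% to 18% is one end of that range. It should not be read as the expected loss, because the documents give no recovery times and set no power target for this outcome.

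The primary outcome, adequate sedation by Ramsay score, is not touched. The point is worth settling before data collection, because an Aldrete time that was not recorded cannot be recovered later.

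**What to change.** In section 14 and in section 17.a (Sedation induction and monitoring), give the same single end for duration of sedation: the first scheduled 5-minute check at which the modified Aldrete score equals its recorded pre-sedation value with no later ketamine dose, whether or not casting is finished.

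Unless the data sheet already does so, record the modified Aldrete score and its time on the existing 5-minute grid, and continue to discharge from sedation; the scheduled Ramsay scoring stops when the reduction is complete.

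Keep the sedating physician's note as a separate, named outcome: time to fitness for discharge from sedation. This changes what is measured and reported, not how any child is managed.

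The cost is wording in two places and one extra column of bedside scoring by personnel who already score every 5 minutes. The downsides are slightly more work during casting and recovery, and recovery times known only to the nearest 5-minute check. The start of the clock also needs one statement, but that is a separate correction.
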